**Truncal ultrasound guided regional anesthesia for implantation and revision of
AICDs and pacemakers in pediatric patients**

NCT04184349

Version Date: 12/19/2019

Title: Truncal ultrasound guided regional anesthesia for implantation and revision of AICDs and pacemakers in pediatric patients.

PI: [name] (Anesthesiologist)

Co PIs: [name] (Electrophysiologist), [name] (Electrophysiologist), [name] (Anesthesiologist), [name] (Anesthesiologist), [name] (Anesthesiologist), [name] (Anesthesiologist)

Population: Children undergoing pacemaker and/or Automatic Implantable Cardioverter Defibrillator implantation at Children's Memorial Hermann Hospital

Study Duration: Data will be collected from procedure for 48 hours

Purpose

The purpose of this study is to determine the efficacy and safety of truncal blocks for pacemaker and Automatic Implantable Cardioverter Defibrillator implantation in children

Hypothesis Truncal block is effective, safe and feasible for implantation of AICDs and pacemakers in children.

Research Design and Procedures to be Used

Written consent for the study will be obtained from a parent. We will also obtain consent from the patient if they are older than 10 years together with their parents.

The patients will be simply randomized by a pre-determined computer generated random numbers and allocated to one of two groups. The group allocation (LA group or B group) will be concealed in sealed opaque envelopes that will be opened after enrollment of the patients. In one group (the LA group), only the local anesthetic infiltration will be performed. In the block group (the B group), PECS and TTP blocks will be performed. The ultrasound-guided nerve blocks will be performed by the anesthesiologist after induction of anesthesia and endotracheal intubation. The left upper extremity angiogram will be performed prior to block to ensure the correct side for the implant. The local anesthetic group will have wound infiltration as routine care by the electrophysiologist at the time of wound closure. Both of these blocks have been used successfully in our institution and the purpose of the study is to prospectively evaluate whether there is a decrease in amount of narcotic medications need and track complications. There is no deviation from the standard of care as currently practiced.

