The adjunctive medication protocol will include scheduled alternating ibuprofen and tylenol unless contraindicated by renal impairment. Both groups of patients will also have oral oxycodone available as needed for moderate breakthrough pain and IV morphine for severe pain. The total dose of local anesthetic for group B will be same as that of group LA.

Primary outcome: We will compare the two groups on their total narcotic dose in milligram morphine equivalents (MME) needed for 48 hours after procedure. This is calculated as intravenous fentanyl (mcg) x0.03+intravenous hydromorphone (mg)x20+intravenous morphine(mg)x3+[number of oral oxycodone 5 mg/acetaminophen 325 mg tabs equivalents]. The 48 hour mark is picked since the local anesthetic duration for either local infiltration or block is 6-12 hours and most patients would be discharged prior to the 48 hour mark. This also allows for sufficient time for complications to develop and tracked as secondary outcomes.

Secondary outcome: VAS pain score in PACU, incidence of pruritus, nausea/vomiting, respiratory depression, local anesthetic toxicity and pneumothorax, these complications would arise early in the post procedure period but would be tracked for 48 hours.

Statistical Analysis

Data will be analyzed within one month after completion of data collection for all enrolled patients. The de-identified data will be uploaded to PI's UTH-Share account and shared with the statistician. We will report the summary statistics of demographics and disease-related characteristics for two groups. The primary endpoint, amount of morphine equivalent administered intra-operative and during the first 24 hours after procedure, will be summarized as median and inter-quartile, and depicted as side-by-side boxplot. Comparison between two groups will be evaluated by Wilcoxon rank sum test. We will report the incidence rates of side effects including pruritis and nausea, as

well as complications including local anesthetic toxicity and pneumothorax. The Wald test will be used for comparing incidence rates between two groups.

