At our institution we performed 24 implants in the last 2 years (aicd/ppm, external, 4 were lead revisions, generator changes or pocket revisions. The most common approach used is the left intra-clavicular subcutaneous (pre-pectoral). We anticipate at least 12 patients per year going forward. Based on a 5% two-sided two-sample t test, the size of 12 patients per group provides the power of 94% for detecting difference for effect size 1.5 assuming that the primary endpoint follows a normal distribution

Data and Safety Monitoring:

Both groups will be followed for signs of local anesthetic toxicity, pneumothorax or infection, these will be reviewed at quarterly intervals with the cardiologist/anesthesiologist PIs.

Risks and Potential Benefits

The risks of wound infiltration (LA group) is the potential use of higher doses of narcotic which is associated with more nausea, pruritis and potential for respiratory depression. The block groups use has the risks of insufficient analgesia with the need for rescue medications, the use of a longer block needle has the theoretical risk of injury to deeper structures such as the lung but the use of ultrasound and experience with ultrasound of the anesthesiologist makes it a minimal risk. Risks with either technique are those associated with any injection: infection, bleeding and damage to surrounding structures. Both groups have the risk of local anesthetic toxicity.

The benefit of the block group is the improved analgesia and decrease in the narcotic dose needed with a resulting decrease in narcotic associated side effects.

The secondary outcomes will be incidence of pruritus, nausea/vomiting

Importance of Knowledge That May Be Reasonably Expected To Result

Truncal ultrasound guided blocks are gaining popularity due to their efficacy in the adult population for implantation of pacemakers and AICDs and so far there is a lack of reports of these being used in the pediatric population. Based on our experience with effectiveness of truncal blocks so far we anticipate encouraging other centers to integrate this modality and offer better pain control to their patients.

Ethics

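### The two definitions of the primary endpoint conflict, and the one that is analysed includes intra-operative opioid given before group LA has any local anesthetic, so it cannot by itself show better postoperative pain control

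*Combined protocol and SAP*

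**What the plan says.** The endpoint is defined twice.

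- **Primary outcome paragraph:** the groups are compared on "total narcotic dose in milligram morphine equivalents (MME) needed for 48 hours after procedure". Intra-operative opioid is not mentioned.
- **Statistical Analysis:** the primary endpoint is the "amount of morphine equivalent administered intra-operative and during the first 24 hours after procedure", compared by one Wilcoxon rank sum test.

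The timing of local anesthetic is set out under Research Design and Procedures to be Used.

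- **Group B:** "The ultrasound-guided nerve blocks will be performed by the anesthesiologist after induction of anesthesia and endotracheal intubation". An angiogram to confirm the side comes before the block.
- **Group LA:** "In one group (the LA group), only the local anesthetic infiltration will be performed". On when this happens: "The local anesthetic group will have wound infiltration as routine care by the electrophysiologist at the time of wound closure".

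The dose does not differ: "The total dose of local anesthetic for group B will be same as that of group LA". The Primary outcome paragraph gives a duration of 6-12 hours for either technique.

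No separate test of intra-operative or postoperative opioid is planned. The only pain score is the VAS in PACU, and no test is named for it.

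**The concern.** The analysed total joins two periods in which the groups are contrasted differently. Between the block and wound closure, group B has local anesthetic and group LA has none. From closure onward, both groups have it. A difference in the first period answers whether a block saves opioid during surgery compared with no local anesthetic. A difference in the second bears on how a block given earlier compares with infiltration given at closure.

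If only the sum is tested, a significant result does not show which period produced it. It could come from opioid saved in anesthetised children before the comparator was given. A null result is also ambiguous, because sparing during surgery could be offset by a block that wears off sooner after it. At stake is the use the sponsor foresees for the result. The section on the importance of the knowledge expects other centers to adopt blocks and "offer better pain control to their patients", and the total alone cannot carry that message for the postoperative period.

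**Working it through.** **1. The two definitions side by side.** They differ in two ways: where the postoperative window ends (48 or 24 hours), and whether intra-operative opioid counts. Only the second raises the timing problem. The MME formula does not settle the matter. It sits in the Primary outcome paragraph and includes intravenous fentanyl and hydromorphone, although the as-needed drugs listed just above it are oxycodone and morphine.

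**2. Which opioid falls in the unequal period.** The documents give no block time relative to incision. A block that follows induction and an angiogram to confirm the side is, by inference, given before incision. Opioid at induction precedes local anesthetic in both groups, and some may be given in the room after closure infiltration. So most of the operation, but not every intra-operative dose, falls in the unequal period.

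**3. The scale in the protocol's units.** The factors are 0.03 per mcg of intravenous fentanyl and 3 per mg of intravenous morphine. The fentanyl difference is an assumption.

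- 100 mcg x 0.03 = 3 MME, the same as 1 mg of morphine (1 x 3 = 3).
- 200 mcg x 0.03 = 6 MME, the same as 2 mg of morphine (2 x 3 = 6).

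**4. The plan's power figure.** For 12 per group, effect size 1.5 and a two-sided 5% t test, the degrees of freedom are 22 and the noncentrality is 1.5 x sqrt(12/2) = 3.67. Exact power is 93.9%, which matches the stated 94%. The plan does not say which of the two definitions the 1.5 refers to.

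**5. Can the total be significant with no postoperative effect?** Let the intra-operative effect be *d* standard deviations, *k* the ratio of postoperative to intra-operative SD, and *r* their correlation. With a postoperative effect of zero, the effect size of the total is

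*d* / sqrt(1 + *k*² + 2*rk*).

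For *d* = 1.5, *k* = 1 and *r* = 0 this is 1.5 / sqrt(2) = 1.06. In 20,000 simulated trials of 12 per group, the exact Wilcoxon test (reject if U is at most 37 or at least 107; true size 4.5%) was significant for the total in about 66%. With *k* = 0.5, 1 or 2 and *r* = 0, 0.3 or 0.5:

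| Assumed intra-operative effect | Total significant | Postoperative MME alone significant |
|---|---|---|
| 1.0 SD | 13-51% | 4-5% |
| 1.5 SD | 24-86% | 4-5% |
| 2.0 SD | 38-98% | 4-5% |

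These inputs, including bivariate normal MME, are not in the documents. The middle column is power to detect a real difference in the total, not a false-positive rate. The last column follows from setting the postoperative effect to zero, so it does not test carry-over.

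**6. Carry-over.** The block's 6-12 hours start before surgery, and those of infiltration start at closure. Length of surgery is not stated. If it were 2-4 hours (assumption), group B would have used between 2/12 = 17% and 4/6 = 67% of its duration by closure; this range pairs the extremes. Any extra opioid given to group LA during surgery may still act in PACU. Both effects would work against the block in early postoperative use.

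**The case against.** The strongest defence is that the total is a sound randomised comparison of two whole strategies as the institution practises them. Under Research Design, the stated aim is to see whether less narcotic is needed, and the risk section ties narcotic dose to nausea, pruritus and respiratory depression. Total peri-operative opioid fits that aim, and separating technique from timing is a choice of estimand. This stands: the total is not invalid.

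It can also be said that the Primary outcome paragraph is already postoperative, so the problem disappears if that definition governs. This stands too, and it is why reconciling the two definitions comes first. As written, however, the section that names the test uses the other definition.

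A third objection is that postoperative MME is itself affected by what happened during surgery, so splitting the total does not isolate block technique from its earlier timing. That is correct, and it limits what the change can achieve.

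A reader might infer that the plan commits itself to concluding that the block controls pain better than infiltration. The documents do not say so. The sentence about better pain control is an expectation based on the institution's experience, and it does not mention infiltration.

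**Conclusion.** The concern holds in a limited form. The two primary-endpoint definitions conflict. The one attached to the test mixes a period of block against no local anesthetic with a period in which both groups have been treated. A significant total could therefore arise without any postoperative benefit, and alone it cannot show better postoperative pain control.

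How likely this is cannot be determined. The documents give no means, SDs or correlation for the two MME components, no fentanyl doses and no length of surgery. The 3-6 MME and the simulated percentages show only that the mechanism can matter at 12 per group. The conclusion also rests on the inference that the block precedes incision.

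A reader might go further and infer that a positive total would be spurious, or that intra-operative sparing is the likely explanation for one. The documents support neither. A difference in the total would be a real difference between strategies, and nothing in them shows which period would drive it.

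**What to change.** 1. Bring the Statistical Analysis into line with the Primary outcome paragraph: make postoperative MME the single primary endpoint, over one window with a stated start and end, and use the same wording in both places.
2. Name intra-operative MME as a secondary endpoint with the same Wilcoxon test, and the combined total as a further secondary.
3. Record block and closure times if the data sheet, which is not among the documents, does not already capture them. The Ethics section says the sheets are destroyed after transfer, so times left off may be hard to recover.
4. Word the conclusions as block after induction versus infiltration at closure. Note that residual intra-operative opioid and the earlier start of the block's 6-12 hours may affect early postoperative use.

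The cost is a change of analysis wording and at most two times per child. The opioid data are already needed for the endpoint as analysed. The downside is a less simple headline, because the components must be read together. The timing of either injection and the number of patients need not change.

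### The Wald test planned for side-effect and complication rates is a large-sample method used with about 12 patients per group; in its unpooled form the type I error can reach about 9%

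*Combined protocol and SAP*

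**What the plan says.** The secondary outcomes, apart from the pain score, are binary: "incidence of pruritus, nausea/vomiting, respiratory depression, local anesthetic toxicity and pneumothorax". The Statistical Analysis section says that the incidence rates of side effects and complications will be reported, and then: "The Wald test will be used for comparing incidence rates between two groups".

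That sentence is the whole specification. It does not say whether the test is on the risk difference (unpooled or pooled variance), the log odds ratio or the log relative risk. It gives no significance level, no rule for empty cells and no exact alternative.

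Three other places bear on it:

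- The sample-size paragraph, just before Data and Safety Monitoring, plans "the size of 12 patients per group". It states the level only for the primary endpoint: "Based on a 5% two-sided two-sample t test".
- Research Design and Procedures to be Used: "The patients will be simply randomized by a pre-determined computer generated random numbers and allocated to one of two groups". Nothing in this forces a 12/12 split.
- Risks and Potential Benefits expects from the block a "decrease in the narcotic dose needed with a resulting decrease in narcotic associated side effects".

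**The concern.** A Wald statistic divides an estimated effect by its estimated standard error and refers the ratio to the normal distribution. With a dozen patients per arm and few events, both the standard error and the normal approximation are poor. The unpooled risk-difference form is the most exposed: an arm with no events contributes zero variance, so the standard error is too small in exactly the tables that look most striking.

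The protocol predicts fewer opioid side effects with the block, and this is the only between-group test planned for them. If nausea or pruritus occurs in about 10% of patients or more, a contrast of three events against none could be reported as a significant benefit when an exact test at the same level would not support that.

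**Working it through.** **Inputs.** From the documents: 12 per group, hence 24 in total; simple randomization. Assumed: two-sided 5% for the incidence comparisons; the Wald form; all event rates, since the documents give none.

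**The plan's own figure.** The only design figure stated is the primary-endpoint power of 94%. With noncentrality 1.5 × √(12/2) = 3.674 and 22 degrees of freedom, the noncentral t gives 93.9%. It reproduces. No design figure is given for the incidence comparisons.

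**One table under different readings: 0/12 versus 3/12.**

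- Unpooled: difference 0.25; SE = √(0 + 0.25 × 0.75/12) = 0.125; z = 2.00; p = 0.0455.
- Pooled: common rate 3/24 = 0.125; SE = √(0.125 × 0.875 × 2/12) = 0.135; z = 1.85; p = 0.064.
- Log odds with 0.5 added to each cell: ln[(3.5/9.5)/(0.5/12.5)] = 2.220; SE = √(1/3.5 + 1/9.5 + 1/0.5 + 1/12.5) = 1.572; z = 1.41; p = 0.158.
- Boschloo (two-sided, twice the smaller one-sided value): p = 0.126.
- Fisher: 2 × C(12,3)/C(24,3) = 2 × 220/2024 = 0.217.

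Only the unpooled reading is significant.

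**Type I error.** For a common true rate π and arm sizes n and m, sum Bin(a; n, π) × Bin(b; m, π) over every table (a, b) with |z| > 1.96, counting undefined tables as non-rejections. For simple randomization, repeat for each split k versus 24 − k (k = 1 to 23) and weight by Binomial(24, 0.5). A 12/12 split has probability C(24,12)/2²⁴ = 16%.

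| True rate | Unpooled, 12/12 | Unpooled, averaged over splits |
|---|---|---|
| 2% | 0.2% | – |
| 5% | 2.1% | – |
| 8% | 4.9% | 3.6% |
| 10% | 6.6% | 5.0% |
| 15% | 9.0% | 7.6% |
| 20% | 9.3% | 8.5% |
| 50% | 6.6% | 8.1% |
| Maximum | 9.4% | 8.5% |

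The error exceeds 5% at true rates of about 8% to 92% with 12/12, and of about 10% to 90% when averaged.

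| Form | Maximum, 12/12 | Maximum, averaged |
|---|---|---|
| Unpooled | 9.4% | 8.5% |
| Pooled | 6.4% | 6.0% |
| Log odds with 0.5 added | 2.6% | 3.1% |

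**How often the conclusion changes.** At 12/12 the unpooled Wald test and Boschloo's test disagree only at 0 vs 3, 1 vs 5, 3 vs 8 and their mirrors (arms exchanged, or events exchanged with non-events). In each, Wald rejects and Boschloo does not. At 0 vs 4 both reject (Boschloo p = 0.045).

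The 0 vs 3 example also depends on the split: 0/10 vs 3/14 gives p = 0.051 and 0/14 vs 3/10 gives p = 0.038. It is significant whenever the zero-event arm has 11 to 21 patients, which is 73% of simple randomizations.

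**No events in either arm.** Both risk-difference forms become 0/0. That yields no result, but also no false conclusion.

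**The case against.** The strongest reply is that the 9% belongs to a form the plan never names. That is true. At 12/12 the pooled form peaks at 6.4%, and log odds with 0.5 added never exceeds 5%. But the protocol permits all of these readings, and on 0/12 versus 3/12 they give p-values from 0.0455 to 0.158. A prespecified test should not leave that choice until the data are seen.

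Second, the inflation does not reach rare complications. This also stands. For pneumothorax or local anesthetic toxicity at rates of a few percent, the unpooled test is conservative. The concern is with nausea, pruritus and perhaps respiratory depression, and only if their rates are about 10% or more.

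Third, 12/12 is not assured, so 8.5% is the fairer maximum for this design. Agreed; it is still well above 5%.

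Fourth, the practical effect is small. With equal true rates, the chance of a 12/12 table that unpooled Wald rejects and Boschloo does not is 5.1% at a 10% rate, 6.1% at 15% and 3.4% at 30%, per outcome. This supports a minor rating but does not justify keeping the test.

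Finally, pairing Boschloo with a Newcombe interval can give conflicting messages. At 3/12 versus 8/12, Boschloo gives p = 0.064 while the interval runs from about 0.02 to 0.67. At 12/12 this conflict occurs only there and at its mirror. It is a real drawback of the suggested wording, and one stated rule on which result governs deals with it.

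**Conclusion.** The concern holds and is minor. The plan prescribes a large-sample test for comparisons of about 12 against 12 without naming its form. Under the unpooled risk-difference form at an assumed two-sided 5% level, the type I error reaches 9.4% at 12/12 and 8.5% averaged over simple randomization, and three events against none at 12/12 is declared significant. This requires true event rates of roughly 10% or more, which is an assumption.

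Only the secondary incidence comparisons are affected. The primary analysis, the sample size, the reporting of incidence rates and the quarterly complication review are not.

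**What to change.** Replace the Wald sentence in the Statistical Analysis section with wording such as:

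> Incidence of each side effect and complication will be compared with Boschloo's unconditional exact test (two-sided 5%), and the risk difference reported with a Newcombe 95% CI. If neither group has an event, counts and exact intervals are reported without a test.

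Add that the exact test decides significance if the two disagree. Fisher's exact test is an acceptable alternative if named in advance.

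The change is confined to the Statistical Analysis section; sample size, data collection and the primary analysis stay as they are. The price is nominal power, shown here for assumed true rates of 10% versus 40%:

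| Test | Power, 12/12 | Power, averaged over splits | Maximum type I error, 12/12 |
|---|---|---|---|
| Unpooled Wald | 51% | 47% | 9.4% |
| Boschloo | 38% | 33% | 4.5% |
| Fisher | 23% | 27% | 2.3% |

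The averaged power uses splits with 7 to 17 patients in one arm, which carry 97.7% of the weight. Part of Wald's apparent advantage comes from its inflated error rate.

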The study has obtained departmental IRB approval and is seeking institutional IRB approval. Given very positive results from the adult population, we believe delaying this study will deprive large groups of children at other institutions from receiving a pain management technique that will improve their comfort and decrease the amount of narcotic needed.

The consent and assent will be explained to family and patient and alternatives which include no randomization will be offered.

A linking log will be used to deidentify data and a data sheet have been attached for review. The data sheets will be securely destroyed as soon as deidentified data is transferred to a electronic form on a secure server. The linking log will be stored in a locked cabinets within a locked office at the medical school.

Any complications will be reviewed quarterly with the EP cardiology/anesthesiology group and will be referred for departmental quality review if there is an increase in the number of complications compared to current base line when both the pain management injections are currently performed as standard of care.

References

1. Miller, Marc ; Garg, Jalaj ; Salter, Benjamin ; Brouwer, Thomas ; Mittnacht, Alex ; Montgomery, Morgan ; Honikman, Rafael ; Arkonac, Derya ; Choudry, Subbarao ; Dukkipati, Srinivas ; Reddy, Vivek ; Weiner, Menachem. Feasibility of subcutaneous implantable cardioverter-defibrillator implantation with opioid sparing truncal plane blocks and deep sedation. *Journal of Cardiovascular Electrophysiology*, Jan 2019, Vol.30(1), p.141
2. (Bashandy, GM and Abbas, DN. Pectoral nerves I and II blocks in multimodal analgesia for breast cancer surgery: a randomized clinical trial. *Reg Anesth Pain Med*. 2015; 40: 68–74;
4. Raza, Syed M. ; Vasireddy, Appa Rao ; Candido, Kenneth D. ; Winnie, Alon P. ; Masters, Robert W. A complete regional anesthesia technique for cardiac pacemaker insertion. *Journal of Cardiothoracic and Vascular Anesthesia*, 1991, Vol.5(1), pp.54-56

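### The only criterion for escalating complications compares an arm-blind count with an unquantified baseline that already contains block cases, so it barely responds to harm inherent to the block

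*Combined protocol and SAP*

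**What the plan says.** **Escalation (Ethics).** Complications are reviewed quarterly by the EP cardiology and anesthesiology group. They go on to departmental quality review under one condition: "if there is an increase in the number of complications compared to current base line when both the pain management injections are currently performed". The same sentence describes both techniques as standard of care. No baseline count, rate, period or mix of techniques is given, and no arm is named.

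**Review (Data and Safety Monitoring).** "Both groups will be followed for signs of local anesthetic toxicity, pneumothorax or infection, these will be reviewed at quarterly intervals". The reviewers are the cardiologist and anesthesiologist PIs. The section does not say whether events are tabulated by arm, and it attaches no action to the review.

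**Between-group comparison (Statistical Analysis).** "The Wald test will be used for comparing incidence rates between two groups". The section places all analysis within a month after data collection is complete.

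**Prior use of the block (Research Design).** "Both of these blocks have been used successfully in our institution".

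**Volume (sample size paragraph).** "At our institution we performed 24 implants in the last 2 years". At least 12 patients a year are expected, and the design has 12 per group.

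**The concern.** Safety is part of both the stated purpose and the hypothesis, the participants are children, and the protocol notes a lack of pediatric reports. Risks and Potential Benefits names different risks for the two arms: injury to deeper structures such as the lung for the block, and opioid effects for local infiltration. An escalation rule should respond when one technique does worse than the other.

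This rule is poorly placed to do so, for two reasons:

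- The baseline comes from a period when the site was already using both techniques. If the block itself causes more complications, the baseline holds them too, and the trial need not look worse.
- The count names no arm. Read naturally, it is a total, so more events in the block group and fewer in the LA group can cancel.

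The randomized LA group, the one comparator free of these problems, enters only in the final analysis. At stake is whether an excess in the block group would be escalated while children are still being enrolled.

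**Working it through.** **Plan's own figure.** The plan gives no operating figure for the safety rule. Its one design calculation is 94% power for a two-sided 5% t test with 12 per group and effect size 1.5. The exact noncentral t (22 df, noncentrality 1.5 × √(12/2) = 3.67) gives 93.9%, so it reproduces. Only the 12 per group is used below.

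**Inputs from the documents.** 12 patients per arm; 24 implants in two years; both techniques in use during the baseline.

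**Assumptions.** The complication rates; a baseline of 24 implants; an even split of techniques in it unless stated; independent events; one look when all 24 patients are in. Repeated quarterly looks would change the figures.

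**Formulas.**
- Trial total T = Bin(12, pLA) + Bin(12, pB). Baseline total H = Bin(24 − m, pLA) + Bin(m, pB), where m is the number of block cases in the baseline.
- The plan's rule fires with P(T > H).
- A concurrent check fires with P(B count > LA count), 12 against 12.

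**Harm inherent to the block, even baseline (m = 12).** At 2% and 20%, the expected trial count is 12 × 0.02 + 12 × 0.20 = 2.64, and the expected baseline count is also 2.64. T and H then have the same distribution, so P(T > H) = (1 − P(T = H))/2, which cannot exceed one half however large the harm. Here P(T = H) = 0.193, and (1 − 0.193)/2 = 0.40. With 2% in both arms the tie probability is 0.475, giving 0.26. With 5% in both it is 0.279, giving 0.36.

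| LA rate | Block rate | Plan's rule, P(T > H) | Concurrent, P(B > LA) |
|---|---|---|---|
| 2% | 2% | 0.26 | 0.17 |
| 5% | 5% | 0.36 | 0.29 |
| 2% | 10% | 0.37 | 0.63 |
| 2% | 20% | 0.40 | 0.88 |
| 5% | 15% | 0.40 | 0.68 |
| 5% | 25% | 0.42 | 0.88 |

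**Other baseline mixes.** Over the four unequal-rate rows, a baseline with 75% block cases fires at 0.24 to 0.30 despite a true block excess. With 25% block cases it fires at 0.49 to 0.63.

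**Offsetting arms.** Take a baseline of 10% for both techniques, and trial rates of 2% in LA and 18% in the block group. The expected totals match: 24 × 0.10 = 2.4 and 12 × 0.02 + 12 × 0.18 = 2.4. The rule fires at 0.40.

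**Excess new in the trial.** If the baseline carries the LA rate throughout, the rule fires at 0.62 to 0.85 over the same four rows. Comparing only block patients with 12 baseline block cases gives 0.63 to 0.88. The absence of an arm split alone therefore costs 1 to 4 points; the mixed baseline is the larger fault.

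**Limit of 12 per arm.** Two-sided Fisher p is 0.093 for 4 v 0 events and 0.037 for 5 v 0.

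**The case against.** The rule has a coherent purpose: to check whether care in the trial is worse than current practice. The protocol says it does not depart from standard care, so a baseline containing both techniques fits that question, and between-group safety is analyzed at the end. This stands as a reason to keep the rule. It does not supply a concurrent signal about the block.

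Three stronger readings are tempting, and the documents do not support them.

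- *Harm could not be attributed to an arm.* That describes the wording of the trigger, not the trial. Both groups are followed, no blinding of the reviewers is described, and they would see about 12/4 = 3 new patients a quarter. Even a pooled count is an inference from the absence of any named arm.
- *The referral rule is the only safety action.* Every complication is reviewed quarterly without condition. The baseline governs only the further step of referral.
- *A count from 3 patients is set against a count from 24.* The baseline period is not stated, and expected yearly volume resembles past volume. Over equal periods, counts approximate rates. The fault is the missing denominator, not a demonstrated mismatch.

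It is also fair to say that 12 per arm limits any rule. A by-arm table cannot serve as a test, and a referral prompted by an LA excess is proper protection for those children, not a defect.

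**Conclusion.** The point holds in this limited form: the sole escalation criterion uses an undefined, mixed-technique baseline, names no arm and leaves out the concurrent control. If the excess is inherent to the block and the baseline is evenly mixed, the rule fires at 0.37 to 0.42, against 0.26 to 0.36 when the arms do not differ, so it barely separates the two. The concurrent count gives 0.63 to 0.88 against 0.17 to 0.29.

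These figures depend on assumed rates and an assumed baseline of 24 implants. The weakness grows with the share of block cases in the baseline and shrinks if they were few or if the excess is new in the trial. The structural point does not depend on the rates: with equal numbers and the same even mix of techniques, the rule cannot fire more than half the time. The plan should be changed, because a better comparison is available from data already being collected.

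**What to change.** Keep the referral step in Ethics and add to it:

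1. At each quarterly review, tabulate cumulative complications by allocated group as events over patients treated. Include infection (listed in Data and Safety Monitoring) and respiratory depression (a secondary outcome).
2. State the baseline as events per implant, with its period, and by technique where known.
3. Compare the block group with the concurrent LA group as well as with that baseline. An excess in either group on either comparison prompts referral.
4. Bring suspected local anesthetic toxicity or pneumothorax to the same reviewers when it occurs, not at the next quarterly meeting.

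The cost is a wording change, a one-page table each quarter and an occasional extra meeting, all by people already named. There are three downsides. Reviewers see events by arm. The comparison is descriptive at this size, and the text should say so. Chance referrals also rise: with equal arms, a difference of at least one event in either direction has probability 2 × 0.173 = 0.35 at 2% and 2 × 0.291 = 0.58 at 5%. If that burden is too high, the team can state in advance a larger difference in counts. For example, requiring the block count to exceed LA by at least two, P(B − LA ≥ 2), gives 0.66 at 2% and 20%, against 0.02 to 0.07 with equal rates of 2% to 5%.
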